8.5. Statistical analysis set

All patients who met the inclusion and exclusion criteria were considered eligible for recruitment.

The two analysis sets in this study are defined as follows:

- The full analysis set (FAS) population analysis set will contain all eligible cases and shedding cases, but does not include culling cases.
- The Compliance (PP) population analysis set will include all subjects in the FAS analysis set with no significant deviation from the program.

Intention-to-treat and conformity analysis sets should be used to analyze the primary efficacy endpoints. The main analysis will be based on the PP analysis set. FAS analysis was regarded as supportive analysis.

9. Device Description

EndoAngel

Version: EA 2301

10. Abbreviations

Abbreviations	Full Name	Chinese
AE	Adverse Event	不良事件
CFDA	China Food and Drug Administration	国家食品药品监督管理总局
CNDA	China National Drug Administration	国家食品药品监督管理总局
CRF	Clinical Record File	病例报告表
CTCAE	Common Terminology Criteria for Adverse Events	不良事件常规评价标准
EC	Ethical Committee	伦理委员会
ICD	Informed Consent Document	知情同意文件
ICF	Informed Consent Form	知情同意书

ITT	Intention to Treat	意向治疗分析集
PP	Per Protocol	符合方案集
SAE	Serious Adverse Event	严重不良事件
EUS	Endoscopic ultrasonography	超声内镜
EUS-FNA	Endoscopic Ultrasound Guided Fine Needle Aspiration	超声内镜引导下细针穿刺活检

11. References

- [4] *Cancer incidence and mortality statistics worldwide and by region*. Available: <https://gco.iarc.fr/today/data/factsheets/cancers/13-Pancreas-fact-sheet.pdf>

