6.4 Suspension and withdrawal

Patients who were screened and confirmed to be eligible for the study, signed the informed consent and completed the randomization were considered as enrolled. If serious program deviation, withdrawal, or death occurs, the subject study is considered to be suspended. If the subject discontinues the study after obtaining informed consent, the data before the discontinuation will still be included in the study-related analysis.

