6.4.3 Replacement

Subject will be deemed to have commenced the study upon completion of the informed consent process, and any subject who has been discontinued prior to or during the EUS examination will not subsequently be replaced by other subjects.

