7.5. Risk minimization

In this study, when there are bugs in the software, doctors can still operate under their own judgment without affecting conventional diagnostic and treatment measures, greatly reducing the risk of the test.

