8.3. Hypothetical test

The main assumptions are:

1. The use of EndoAngel can reduce the missed scanning rate of adjacent important anatomical structures in pancreatic endoscopic ultrasonography.
2. The use of EndoAngel can improve the the detection rate of Pancreatic lesions.

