8.4. Sample Size Calculation

We mainly studied the effect of EndoAngel on the quality of EUS scanning for physicians. Therefore, data collection and analysis were conducted for the main effect. It is expected that a total of 285 subjects will be enrolled. Assuming the missed scanning rate of adjacent important anatomical structures in experimental group is 8%, the missed scanning rate of adjacent important anatomical structures in control group is 20%. Bilateral significance level 5% (alpha =5%), assurance 80% (beta =20%), shedding rate 10%, Expected to enroll 285 patients in total.

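### The main analysis of a superiority hypothesis is per protocol, and because its exclusion terms are undefined, neither analysis set is sure to hold all randomised subjects

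*Combined protocol and SAP*

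**What the plan says.** Section 8.5 defines two sets. The FAS "will contain all eligible cases and shedding cases, but does not include culling cases". The PP set is "all subjects in the FAS analysis set with no significant deviation from the program". It then ranks them: "The main analysis will be based on the PP analysis set. FAS analysis was regarded as supportive analysis". The same section says an intention-to-treat set should be used for the primary endpoint, but defines no set under that name.

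The first hypothesis in 8.3 is directional: "The use of EndoAngel can reduce the missed scanning rate of adjacent important anatomical structures in pancreatic endoscopic ultrasonography". Section 8.4 sizes it as a two-sided 5% test with 80% power, 8% against 20%, 10% shedding and 285 enrolled. No non-inferiority margin appears.

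Enrolment is at randomisation, before the EUS (3.3, 6.4). Several provisions govern what can happen afterwards:

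- 6.4.1 allows withdrawal before the EUS.
- 6.4.2 allows withdrawal during it, including when the endoscopist does not use the specified instrument.
- 6.4 says that for a subject who discontinues, "the data before the discontinuation will still be included in the study-related analysis", without naming an analysis set.
- 6.4.3 says discontinued subjects "will not subsequently be replaced by other subjects".
- 7.5 says that if the software has bugs, "doctors can still operate under their own judgment without affecting conventional diagnostic and treatment measures".

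**The concern.** In a superiority comparison the main analysis should keep subjects in the arm to which they were randomised. Removing some after randomisation can undo the balance that randomisation gave. Here both removal terms are undefined. Section 6.4 mentions a serious deviation, also without defining it. Two analysts could form different primary sets from the same data. No text says who classifies deviations, or that this is done blind to arm. The operator works with or without AI prompts and so knows the arm.

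Two routes could tie exclusion to arm or outcome:

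- **Non-use of the instrument (6.4.2).** If the instrument meant is EndoAngel, this can arise only in the AI arm. That is one reading of the text.
- **Exclusion criterion 7 (3.2).** It removes patients whose vital structures cannot be observed, which is close to the primary endpoint. It matters only if applied after the EUS has begun; the table in 1.1 places eligibility at screening.

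At stake is whether the primary conclusion keeps the protection of randomisation.

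**Working it through.** **1. The plan's own figure.** Inputs from 8.4: 20% and 8%, two-sided 5%, 80% power, 10% shedding. The unpooled normal formula gives n = (1.960 + 0.842)² × (0.20×0.80 + 0.08×0.92) / 0.12² ≈ 127.3, so 128 per arm and 256 in total. Then 256 / 0.90 = 284.4, so 285. The stated size reproduces; the arithmetic is not in question.

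**2. Effect of exclusions when there is no true effect.** Set both arms to a 20% miss rate, with 142 AI and 143 control subjects. Treat the outcome as yes/no per examination, as 8.4 does (4.1 defines a count per EUS). If a fraction f of an arm is excluded and those examinations miss at rate q, the rate left in that arm is

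(0.20 − f·q) / (1 − f).

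The plan gives no f or q, so all values are assumed. For example, f = 0.05 and q = 0.60 give (0.20 − 0.03) / 0.95 = 0.179. The probability that a two-sided 5% pooled z-test favours EndoAngel, by exact binomial enumeration, is:

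| Exclusions | AI vs control n | q = 40% | q = 60% |
|---|---|---|---|
| None | 142 vs 143 | 2.5% | 2.5% |
| 2% in both arms | 139 vs 140 | 2.5% | 2.5% |
| 5% in both arms | 135 vs 136 | 2.5% | 2.5% |
| AI arm only, 2% (3 subjects) | 139 vs 143 | 3.1% | 3.7% |
| AI arm only, 5% (7 subjects) | 135 vs 143 | 4.1% | 6.5% |
| Control arm only, 2% | 142 vs 140 | 2.1% | 1.7% |
| Control arm only, 5% | 142 vs 136 | 1.5% | 0.8% |

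With AI-only exclusions unrelated to outcome (q = 20%), the probability stays at 2.5% for both fractions. The error therefore moves only when exclusion is unequal and related to outcome, and its direction depends on the arm that loses subjects.

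**3. Power if subjects are kept as assigned.** Suppose 5% or 10% of the AI arm goes unassisted and misses at 20% (assumed). The AI rate becomes 0.95×8% + 0.05×20% = 8.6%, or 0.90×8% + 0.10×20% = 9.2%. The same exact test gives:

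| AI-arm miss rate | All 285 analysed | 128 per arm (after 10% shedding) | n per arm for 80% | Enrolled, 2n/0.9 |
|---|---|---|---|---|
| 8.0% | 84.9% | 80.2% | 128 | 285 |
| 8.6% | 80.1% | 75.0% | 143 | 318 |
| 9.2% | 74.7% | 69.4% | 164 | 365 |

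**The case against.** The strongest reply is that the plan has more safeguards than the criticism suggests, and that no bias is shown.

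- **Blinding.** Section 6.5.2 blinds assessors and says the data analysis team cannot learn the allocation from the medical history. This is the most relevant safeguard. It does not assign deviation classification to those people, and a deviation for not using the device could itself reveal the arm.
- **Retention of dropouts.** The FAS expressly keeps shedding cases. Read with 6.4, the natural meaning is that dropouts stay in the FAS. That stands, but the FAS is only supportive, and culling cases leave both sets.
- **Some rules exist.** Section 3 gives two reasons for exclusion after consent, one restricted in order to limit researcher bias, and 6.4.2 lists events for withdrawal during the procedure. The exact criticism is that 8.5 does not tie its sets to these reasons.
- **A second analysis is planned.** The FAS result would expose a PP–FAS difference, except for subjects culled from both. It could not carry the primary conclusion.
- **The size is assumed.** This is true. The percentages illustrate a mechanism and do not describe the count endpoint of 4.1.

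**Conclusion.** The concern holds and should be fixed before any analysis by arm. It rests on the text: superiority hypothesis, PP main, FAS supportive, and undefined terms that can remove randomised subjects from both sets. Confidence in that is high.

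The possible bias is conditional. It is nil if exclusions are balanced or unrelated to outcome, favours EndoAngel if harder examinations leave the AI arm, and works against it if they leave the control arm. Under the assumed 2% to 5% AI-only exclusions, with excluded examinations missing at 40% to 60%, the chance of a false finding for EndoAngel is 3.1% to 6.5% against 2.5%. The serious rating comes less from these figures than from timing: definitions written once results are known cannot restore the protection of randomisation.

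**What to change.** In 8.5:

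1. Make the main analysis all randomised subjects who started an EUS, in their assigned arm, whether or not the device was used and including stopped examinations. This stops short of every randomised subject because 4.1 divides by the number of EUS. Report randomised subjects with no EUS by arm with reasons, and cover them in a missing-data sensitivity analysis.
2. Limit culling to reasons fixed before randomisation and judged blind to arm. State that intention-to-treat means the set in point 1.
3. State how structures not reached in a stopped examination are counted, and run the alternative count as a sensitivity analysis.
4. Make PP supportive. Define a significant deviation, have deviations classified blind to arm before analysis, and report PP exclusions by arm with reasons.

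The cost is a few sentences and one table of exclusions by arm. With no unassisted AI-arm examinations, 285 still suffices. If 5% or 10% of that arm goes unassisted and the planned shedding occurs, power falls from 80.2% to 75.0% or 69.4%. Holding 80% would then need about 318 or 365 enrolled. The sponsor should state what level of unassisted use it expects and decide on that basis.
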